1.2. Participants

Patients with defined MS (13) were recruited from the MS Centers of Hospitals in the Czech Republic in accordance with the following inclusion criteria: prevailed spastic paraparesis, stable clinical status and treatment in the preceding 3 months determined by neurologist, Expanded Disability Status Scale score (EDSS) ≤ 7.5 (14). The study was powered in order to provide 80% power for weak to moderate effect size (Cohen's $d=0.2-0.5$). 120 people were initially assessed for eligibility, 92 were allocated into three groups; from these 71 participants finished their therapeutic programs. Data of ten patients were discarded upon the visual control, due to the low quality of DTI acquisition resulting in 61 participants entering the central analysis. This sample provides 80% power to detect at $p<0.05$ effects of minimal size $d=0.36$ (weak to moderate effect size). For distribution of participants into groups during the study see Figure 1, for their baseline characteristics see Table 1. All subjects signed an informed

consent form approved by the Ethics Committee of Kralovske Vinohrady University Hospital in Prague (full trial protocol EK-VP/22/0/2014 is available there).

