1.5. White matter integrity

All participants underwent magnetic resonance imaging on a 3T magnetic resonance scanner (Siemens Trio Tim, Erlangen, Germany) using a 12-channel phased-array head coil. The acquisition protocol consisted of T1-weighted and T2-weighted

anatomical scans, and diffusion weighted imaging using spin echo epi sequence with following parameters TR=9100 ms, TE=96 ms, FOV=260x211 mm, 64 contiguous axial slices with 2 mm thickness, b=0 and 1100 s/mm², 64 gradient directions.

For the DTI pre-processing, a combination of FSL tools (FMRIB Software Library, <http://www.fmrib.ox.ac.uk/fslwiki>, version 5.0) and MRtrix3 was used. The data was initially de-noised and corrected by applying the MRtrix dwidenoise function (21) and Gibbs ringing correction (22). The resulting images were visually controlled, and the volumes with low quality were discarded. The 'Eddy current correction' was subsequently applied (23).

In the context of neuroproprioceptive PT, we did not expect changes in a particular area; hence we analyzed FA across the white matter using a global changes of FA as well as FA changes in 48 white matter regions.

FA global change and changes in 48 regions of interest

A diffusion tensor was fitted to each voxel of the brain, and a fractional anisotropy (FA) map was created for each subject (24). The images were further analyzed using tract-based spatial statistics (TBSS) (25). The TBSS routine consisted of three steps: 1) non-linear registration of all FA images to a chosen template – we chose the FMRIB58_FA standard-space image as a target; 2) application of the non-linear registration identified in the first step, affine registration of each subject to MNI152 space and skeletonization of the mean image; 3) thresholding of the mean skeleton (we used 0.3 as a threshold) and a projection of individual subjects FA maps onto the mean skeleton. Primarily, the (global) mean of the projected FA values over the whole skeleton were compared among subjects.

The resulting skeletonized images were parcellated using the ICBM-DTI-81 white- (26) matter labels atlas consisting of 48 regions, and the mean FA value for each region was computed (regions are listed in Table 3).

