1.6. Statistical analysis

The resulting dataset was further analyzed using the non-parametric Wilcoxon test for assessing the difference between visits. Differences between the treatment groups were identified using the Kruskal-Wallis test. All statistical analyses were performed using Matlab (MATLAB version R2018b). Note that the region-wise analysis was considered exploratory so that there was used an uncorrected significance threshold of 0.05 to select the strongest effects for description. Due to the multiple undertaken tests, many of the presented localized effect results can constitute false positive findings, and thus the observed effects serve rather as initial findings calling for independent validation in a follow-up study. The conservative Bonferroni-corrected threshold across 48 regions would correspond to $0.05/48 \approx 0.0001$, which was not reached by any single one of the effects. However, this is to be expected, as the study sample size was not designed for confirmatory testing of such a large set of hypotheses, but rather for global effect testing. This additional exploratory analysis is intended to provide the reader with further information on the presence/absence and spatial distribution of any potential localized effects outside the global hypotheses testing.

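### Regional visit changes are judged only at an uncorrected 0.05 or against a misprinted Bonferroni limit (0.0001 for 0.00104); max-statistic adjusted p-values would use the correlation between regions

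*Combined protocol and SAP*

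**What the plan says.** Section 1.5 (White matter integrity) makes mean fractional anisotropy (FA) over the whole skeleton the primary imaging measure, while stating that "we did not expect changes in a particular area". The skeleton is then divided by an atlas "consisting of 48 regions, and the mean FA value for each region was computed".

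Section 1.6 (Statistical analysis) uses a Wilcoxon test between visits and Kruskal-Wallis between the three groups. For the regions it offers two yardsticks:

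- no correction: "there was used an uncorrected significance threshold of 0.05 to select the strongest effects for description";
- a reference limit: "The conservative Bonferroni-corrected threshold across 48 regions would correspond to $0.05/48 \approx 0.0001", "which was not reached by any single one of the effects".

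It attributes the absence of corrected findings to size: "the study sample size was not designed for confirmatory testing of such a large set of hypotheses". It calls the regional work exploratory, warns that many localized results may be false positives and asks for independent validation. It describes no permutation, step-down, false-discovery-rate or multivariate method.

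**The concern.** Section 1.6 wants the regional analysis to inform the reader about whether localized effects exist and where. Neither yardstick serves that well. An uncorrected 0.05 does not tell the reader whether the list of regions is longer than chance would produce. Bonferroni is valid, but regional changes within one brain are likely to be correlated, and under positive correlation it spends less than its 5%. A failure to reach it is then partly a property of the method, not only of the sample size.

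The Bonferroni figure is also miscalculated. If the statement that nothing reached it was judged against the printed value, regions with p between 0.0001 and 0.00104 were set aside wrongly.

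The one test above the regional level is a signed mean. It has little power when change is confined to a few regions or runs in opposite directions, and the plan does not rule out either.

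**Working it through.** **Inputs.** From the documents: n=61 in the central analysis (section 1.2), 48 regions (1.5), per-region level 0.05 and printed limit 0.0001 (1.6). Assumed: two-sided tests, the signed-rank form of the Wilcoxon test, normal change scores and a common inter-regional correlation ρ. The documents give no ρ, so a range is shown.

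**1. The plan's own figures.** On power, section 1.2 says: "This sample provides 80% power to detect at $p<0.05$ effects of minimal size $d=0.36$ (weak to moderate effect size". For a within-person change, d = (1.960 + 0.842)/√61 = 2.802/7.810 = 0.359. This reproduces. The Bonferroni limit does not: 0.05/48 = 0.00104, and 0.00104/0.0001 ≈ 10.4. The printed limit corresponds to a family-wise level of 48 × 0.0001 = 0.0048.

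**2. What the misprint does to power (n=61, noncentral t).**

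| Limit | d detectable with 80% power | Power at d=0.5 |
|---|---|---|
| 0.00104 | 0.55 | 67% |
| 0.0001 | 0.65 | 41% |

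**3. Chance lists at uncorrected 0.05.** The expected number is 48 × 0.05 = 2.4 at any ρ. Given a shared standard normal factor f, each region passes with probability p(f) = Φ((−1.96 − √ρ·f)/√(1−ρ)) + Φ((−1.96 + √ρ·f)/√(1−ρ)), and the count is Binomial(48, p(f)). Averaging over f:

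| ρ | P(5 or more regions) | 95th percentile of count |
|---|---|---|
| 0 | 9.1% | 5 |
| 0.2 | 12.8% | 6 |
| 0.5 | 15.6% | 10 |
| 0.7 | 14.2% | 14 |
| 0.9 | 10.4% | 18 |

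Simulations with the signed-rank test gave 12–17% for ρ = 0.2 to 0.7. Correlation makes long chance lists longer.

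**4. Max-statistic in place of Bonferroni (visit comparison).** In flip b, multiply each patient's whole vector of 48 changes by +1 or −1 at random and keep the largest absolute statistic M(b). For region j, adjusted p = (1 + number of flips with M(b) ≥ |T(j)|)/(B + 1). Simulated family-wise error with no effect, Bonferroni against max-statistic: 0.035/0.045 at ρ=0, 0.026/0.051 at 0.5, 0.016/0.047 at 0.7, 0.006/0.050 at 0.9. Power per truly changed region at d=0.4 (Monte Carlo error about 2 points):

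| ρ | Bonferroni (0.00104) | Max-statistic | Gain (points) |
|---|---|---|---|
| 0.2 | 32% | 35% | 3 |
| 0.5 | 35% | 43% | 8 |
| 0.7 | 33% | 48% | 15 |
| 0.9 | 33% | 60% | 27 |

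A separate run at d=0.5 gave 62.2→65.7%, 61.3→68.4% and 64.8→76.6% at ρ = 0.2, 0.5 and 0.7: gains of 3.5, 7.1 and 11.8 points. Another, with six regions up and six down by 0.4, gave 35.8→61.2% at ρ=0.9, a gain of 25.4. At ρ=0 the gain is 0–3 points.

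**5. Omnibus tests beside the global mean (power in %, d=0.4).**

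| Scenario | ρ | Global mean | Bonferroni, any region | Max-statistic | Sum of squares |
|---|---|---|---|---|---|
| 6 up, 6 down | 0.5 | 6 | 100 | 100 | 88 |
| 6 up, 6 down | 0.7 | 5 | 97 | 100 | 50 |
| 6 up, 6 down | 0.9 | 4 | 92 | 100 | 28 |
| 4 regions changed | 0.5 | 6 | 65 | 75 | 14 |
| 4 regions changed | 0.7 | 5 | 57 | 72 | 9 |
| 4 regions changed | 0.9 | 7 | 51 | 83 | 11 |

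The smallest adjusted p from step 4 is the max-statistic omnibus test. A permutation sum-of-squares test is a natural alternative, but it is weak for focal change and at high correlation.

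**The case against.** The strongest reply is that section 1.6 already says what a careful reader needs: the regional work is exploratory, false positives are likely, and validation must come from elsewhere. That stands. A description at uncorrected 0.05 under those warnings is a legitimate purpose, and restricting description to adjusted findings would override it.

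Second, a reader might infer that the trial cannot say whether its regional pattern exceeds chance. The documents do not support that. Whether any region passes Bonferroni is itself a valid omnibus test, and the plan reports its result. Step 5 shows that it already has far more power than the global mean in these scenarios, so the gain from the max-statistic is incremental. What remains is that the reported result rests on a misprinted limit.

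Third, a reader might infer that a real finding was dismissed, or that the length of the regional list was never set against chance. Neither can be shown. The regional p-values are not in the documents, and the 0.0001 may be only a slip in writing. If it was applied, the error was conservative and created no false positives.

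Fourth, it is tempting to say that one sign-flip run gives exact answers throughout. It covers the visit comparison only. Exactness needs changes symmetric about zero: with strongly skewed mean-zero changes at ρ=0.5, the t-based max-statistic had family-wise error 0.27 and Bonferroni on t-tests 0.20. The signed-rank test needs the same symmetry, so no new assumption enters. The group comparison needs permutation of group labels; since section 1.1 describes allocation by therapist and device availability, exchangeability there is assumed and not ensured by design.

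**Conclusion.** The point holds as a specific, inexpensive improvement together with one arithmetic correction. The limit should read 0.00104, and the claim that no effect reached it should be rechecked. For the before-after analysis, the max-statistic keeps family-wise error near 5%. It adds about 3–4 points of per-region power over a correct Bonferroni at ρ=0.2, 7–8 at 0.5, 11–15 at 0.7 and about 25 at 0.9.

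These sizes rest on assumed equal correlations, normal changes, effects of d=0.4 to 0.5 and all 61 patients pooled. At low correlation the gain is negligible. Within single arms, at an assumed 20 patients each, max-statistic power per region at d=0.4 in absolute value is only 4–13%, so the method does not rescue arm-specific regional claims. The plan's disclosure of exploratory status keeps this well short of a fatal fault.

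**What to change.** 1. In section 1.6, correct the limit to 0.05/48 = 0.00104 and recheck, against the regional p-values, the statement that no effect reached it.
2. For the before-after analysis, replace the Bonferroni check with max-statistic adjusted p-values: signed-rank statistic, at least 10,000 sign flips of each patient's whole 48-region change vector. Report the smallest adjusted p as the omnibus test beside the global mean. Do not use a sum-of-squares omnibus.
3. From the same flips, report the permutation p for the number of regions below 0.05, next to the 2.4 expected by chance.
4. For the group comparison, run a separate permutation of group labels and state the exchangeability assumption.
5. State the symmetry assumption for the sign flips.
6. Regions may still be described at uncorrected 0.05 as exploratory, with the adjusted p shown beside each.

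Cost: a short extra analysis in Matlab, which the team already uses, on existing data. The price is that some regional effects may look less impressive.

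### The Bonferroni threshold for 48 regions is printed as 0.0001, but 0.05/48 is about 0.001, so the statement that no region reached it needs rechecking

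*Combined protocol and SAP*

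**What the plan says.** Section 1.5 (White matter integrity) makes the whole-skeleton mean FA the main comparison: "Primarily, the (global) mean of the projected FA values over the whole skeleton were compared among subjects". It then divides the skeleton by an atlas: "matter labels atlas consisting of 48 regions, and the mean FA value for each region was computed".

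Section 1.6 (Statistical analysis) calls the regional work exploratory ("Note that the region-wise analysis was considered exploratory") and says that "there was used an uncorrected significance threshold of 0.05 to select the strongest effects for description". It warns that many of the localized results may be false positives and asks for independent validation. As a comparator it then offers a corrected threshold: "The conservative Bonferroni-corrected threshold across 48 regions would correspond to" a value that it works out, and compares with the results, as "0.05/48 \approx 0.0001$, which was not reached by any single one of the effects". The next sentence explains the absence of surviving regions by the sample size, which was set for the global test.

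**The concern.** The expression and its printed value disagree within one sentence. Numerator and divisor are both given, and their quotient is about 0.001, not 0.0001.

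This is more than a cosmetic slip because a result hangs on the number. Failing to reach 0.0001 does not imply failing to reach 0.00104. If the printed value was the one applied, a region could have passed the intended correction and still be reported as failing it. Someone planning the follow-up study would want to know which regions, if any, survive correction, and this sentence is the only place where the plan answers that. The explanation that follows it would then account for a null finding that might not hold at the correct threshold.

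**Working it through.** **Inputs**

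- Nominal level: 0.05 (section 1.6).
- Number of regional tests: 48 (section 1.5, repeated in section 1.6).
- Method: Bonferroni, threshold = α/m (section 1.6).
- Printed result: 0.0001 (section 1.6).

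**Attempt to reproduce the printed figure**

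α/m = 0.05/48 = 0.0010417. This rounds to 0.001 or 0.0010, and no rounding of it gives 0.0001. The ratio is 0.0010417/0.0001 = 10.4.

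**Could another reading give 0.0001?**

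| Reading | Threshold |
|---|---|
| Bonferroni, 0.05/48 | 0.00104 |
| Šidák, 1 − 0.95^(1/48) | 0.00107 |
| One-sided level, 0.025/48 | 0.00052 |
| Stricter level, 0.01/48 | 0.00021 |
| Two sets of 48 pooled, 0.05/96 | 0.00052 |
| Three sets, 0.05/144 | 0.00035 |
| Four sets, 0.05/192 | 0.00026 |
| Five sets, 0.05/240 | 0.00021 |

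The pooled rows are assumptions, since the plan states a family of 48. None of the rows gives 0.0001. Working backwards, 0.05/0.0001 = 500 tests would be needed. Allowing for rounding (0.00005 to 0.00015), the count would have to lie between 0.05/0.00015 = 333 and 0.05/0.00005 = 1000.

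**Effect on the error rate**

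- Bonferroni bound at the printed value: 48 × 0.0001 = 0.0048, against the intended 0.05.
- With 48 independent tests (an assumption), the family-wise error is 1 − (1 − 0.0001)^48 = 0.0048 at the printed value and 1 − (1 − 0.00104)^48 = 0.049 at the correct one.

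**The affected band**

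- Its width is 0.0010417 − 0.0001 = 0.00094, which is 0.00094/0.00104 = 90% of the correct rejection range.
- If no region had any effect, the expected number of the 48 p-values in the band would be 48 × 0.00094 = 0.045 per set of tests. The band fills up only if real effects exist.
- For scale, section 1.2 (Participants) gives 61 analysed participants and a minimal detectable d of 0.36. A one-sample normal approximation gives (1.96 + 0.84)/√61 = 0.359, in line with that figure. On the same approximation, two-sided p-values of 0.00104 and 0.0001 correspond to observed effects of 3.28/√61 = 0.42 and 3.89/√61 = 0.50. The plan uses the Wilcoxon test, so this is only illustrative, but it places the band near the top of the 0.2 to 0.5 range that section 1.2 names.

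**The case against.** The strongest reply is that this is a misprint on which no decision rests. The exact expression stands beside the decimal, so the authors may have compared their p-values with 0.05/48 itself and merely typed one zero too many; any reader can redo the division. The threshold is hypothetical, regions were selected at the uncorrected level, and the section warns openly of false positives. The main test, on global FA, does not use the number. The error is conservative and cannot produce a false claim of significance. The 90% figure is the width of an interval, not a probability. Finally, without regional p-values in the text supplied, the statement could not be checked here even if 0.001 had been printed.

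Most of this stands, and it limits how serious the point is. A misprint is the likeliest explanation, and a slip in the machine reading of the PDF cannot be wholly excluded, although nothing points to one. The absence of regional p-values from the supplied text is not held against the plan. What remains is that the sentence reports a result against a figure that is wrong by a factor of ten, and nothing elsewhere in the documents corrects it or shows that the right value was used.

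**Conclusion.** The point holds: the threshold is wrong as written. For the stated family of 48 tests at 0.05, it is 0.00104, and the printed 0.0001 is 10.4 times too small. This rests only on the two numbers printed in the plan.

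The accompanying statement that no region reached the threshold is not shown to be false. It is unconfirmed for p-values between 0.0001 and 0.00104, and the documents do not reveal whether any region lies there. At worst, a region that passes the correction is described as failing it. The global FA test, the sample size and the rule for selecting regions are unaffected. The number should be corrected because it carries the plan's only multiplicity-corrected conclusion on the regions, but the consequence is limited.

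**What to change.** 1. In section 1.6, replace the printed value with about 0.001 (0.00104), after checking the digit in the source file.
2. Compare the regional p-values already computed with 0.00104, starting with the smallest.
3. If none is at or below 0.00104, keep the statement that no region survived. If one is, name the region and revise both that statement and the sentence that explains the null result.
4. If the between-visit and between-group tests were meant as one family, say so and print the matching divisor; for example, 96 tests give 0.00052.

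The cost is one corrected number and a look at existing output, with no new data and no new analysis.
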